### **Setting**

Hybrid Academic Medical Center

### **Subjects selection criteria**

Patients who meet the following criteria will be included in the study.

- **Inclusion Criteria**

- Aged at least 18 years
  - Ventral Hernia requiring surgical repair

- **Exclusion Criteria**

- Pregnant women
  - Sensitivity to Polysorbate 20

- **Sample Size**

This study will have a sample n=200 (n=50 Fortiva, n=150 Strattice). All participants may not be eligible for the study, so this study may consent up to 100 prospective participants to achieve the 50-participant sample size. This study will serve as a pilot study to compare rates of hernia recurrence and mesh related complications between Fortiva and Strattice. Our group has published research in press showing a 4% hernia recurrence rate for Strattice mesh. Based on an alpha level of 0.05 and a beta of 0.80 and a non-inferior limit of 2% the sample size per group would be 1188. Based on these numbers we would like to do a matched pilot study with a more feasible sample size of 200 participants (n=50 Fortiva(retrospective and prospective), n=150 Strattice(retrospective)).

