### **Goal**

The goal of this research study is to show that Fortiva porcine dermis biologic mesh is equivalent to Strattice biologic mesh with respect to hernia recurrence rates and mesh related complication rates. Fortiva is an FDA cleared (510(k)) hernia mesh that is substantially equivalent to Strattice but at a reduced cost. The goal is to show similar equivalent outcomes to justify the use of Fortiva.

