### **Objectives**

**Primary Objective:** To determine the hernia recurrence rates for RTI Surgical biologic mesh (Fortiva) compared to Strattice

**Hypothesis:** Fortiva mesh will have equivalent rates of hernia recurrence compared to Strattice

**Secondary Objective(s):** To determine the mesh related complications for RTI Surgical biologic mesh (Fortiva) compared to Strattice

**Hypothesis:** Fortiva mesh will have equivalent rates of mesh related complications compared to Strattice

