### **Methods and Measures**

#### **Design**

This study will be a prospective, matched study of patients using Fortiva biologic mesh to determine the rates of hernia recurrence and mesh related complication compared to a retrospective cohort of patients who received Strattice mesh. The indication CLASP surgeons use for biologic mesh use is in contaminated/dirty cases; surgeons are sometimes unable to determine this until they are in the OR. To account for the nature of biologic mesh use in

ventral hernia repair, patients whom an attending surgeon uses Fortiva mesh in the OR when it was not otherwise planned (i.e. the surgeon changed the plan intraoperatively) will be approached in the postoperative space (i.e. follow-up clinic visits or phone calls) to be consented for inclusion in the study. In the event a subject cannot be reached in clinic prior to the end of their standard of care follow-up, a full waiver of consent will be requested to capture all patients and not unnecessarily skew the results. The rates of hernia recurrence and mesh related complications will be compared to determine equivalence. Patients who meet the inclusion and exclusion criteria will be prospectively enrolled to receive a Ventral Hernia Repair (VHR) using Fortiva biologic mesh and will be compared to a retrospective cohort of patients with a VHR that utilized Strattice mesh. All procedures and clinical care have already occurred for the participants who received a VHR with Strattice mesh. Participants will be propensity matched in a 1:3 (Fortiva : Strattice) fashion based on age, sex, and hernia defect size to control for confounding variables.

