### **Analytical Plan**

Results will be analyzed initially using descriptive statistics. Comparison between groups will be done using chi square tests for proportions, and t-tests or ANOVA procedures for continuous variables. Regression analysis will be performed to identify independent outcome predictors. Other inferential statistical analysis will be conducted as appropriate.

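### The goal, hypotheses and design sentence still promise equivalence, but the study is a 50 versus 150 pilot analysed only by difference tests; power 0.80 is also labelled beta 0.80

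*Combined protocol and SAP*

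**What the plan says.** **Aim.** The Goal section states "The goal of this research study is to show that Fortiva porcine dermis biologic mesh is equivalent to Strattice biologic mesh" on recurrence and mesh-related complications, and gives the purpose: "The goal is to show similar equivalent outcomes to justify the use of Fortiva". Under Objectives the primary hypothesis is "Fortiva mesh will have equivalent rates of hernia recurrence compared to Strattice"; the secondary hypothesis makes the same claim for complications. The Design section adds "The rates of hernia recurrence and mesh related complications will be compared to determine equivalence".

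**Size.** The Sample Size text (under Subjects selection criteria) takes a 4% recurrence rate for Strattice and states that with "an alpha level of 0.05 and a beta of 0.80 and a non-inferior limit of 2% the sample size per group would be 1188". It then says "we would like to do a matched pilot study with a more feasible sample size of 200 participants", split 50 Fortiva and 150 Strattice, and calls the study a pilot. Sidedness, allocation ratio and the assumed Fortiva rate behind 1188 are not stated.

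**Analysis.** The Analytical Plan says "Comparison between groups will be done using chi square tests for proportions". It also lists descriptive statistics, t-tests or ANOVA for continuous variables, regression to find outcome predictors, and an open clause on other inference. It names no risk difference, confidence interval, margin, non-inferiority test or equivalence test.

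**The concern.** Three parts of the plan do not fit together. The aim is equivalence. The only limit given is a one-directional non-inferiority limit, attached to a sample size that the study will not have. The named test looks for a difference, and failing to find one is not evidence that two rates are close.

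Because nothing else is specified, a non-significant chi-square is the only named between-group result that could be taken as meeting the goal. The Goal section ties that conclusion to justifying use of the mesh, so a clearly higher recurrence rate could be reported as equivalence.

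The beta label is a separate, minor matter: it is a wrong stated figure, but it changes no decision.

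**Working it through.** **Inputs.** From Sample Size: Strattice recurrence 4%, limit 2% (read as 2 percentage points), alpha 0.05, the 0.80 figure, 1188 per group, and 50 versus 150. Assumed unless stated otherwise: Fortiva recurrence also 4%, independent groups (the 1:3 matching is ignored), no dropout.

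**1. Reproducing 1188.** n per group = (z_alpha + z_power)² × 2 × 0.04 × 0.96 / 0.02² = (z_alpha + z_power)² × 192.

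| Reading | Calculation | n per group |
|---|---|---|
| One-sided 0.05, power 0.80 | (1.645 + 0.842)² × 192 = 1187.05 | **1188** |
| One-sided 0.025, power 0.80 | (1.960 + 0.842)² × 192 | 1507 |
| One-sided 0.05, beta literally 0.80 | (1.645 - 0.842)² × 192 = 123.9 | 124 |

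So 1188 is correct for one-sided 0.05, 1:1 groups, 4% in both and power 0.80 (beta 0.20). The label is the error, not the number.

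**2. 1188 is not an equivalence size.** If the 2-point limit is assumed to apply in both directions, two one-sided tests (TOST) at 0.05 with 80% power need (1.645 + 1.282)² × 192 = 1644.3, or 1645 per group; at 0.025 each, 2018. With 1188 per group, TOST power at 0.05 is about 60%.

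**3. Precision of 50 versus 150.** Expected recurrences: 50 × 0.04 = 2 and 150 × 0.04 = 6.

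- SE = √[0.0384 × (1/50 + 1/150)] = 0.0320.
- Half-width: 1.645 × 0.0320 = 5.3 points (90%); 1.96 × 0.0320 = 6.3 points (95%).
- Newcombe limits at 2/50 versus 6/150: -4.4 to +7.6 points (90%); -5.3 to +9.7 points (95%).
- With an assumed 20% loss by 36 months (40 versus 120): SE 0.0358, half-widths 5.9 and 7.0 points.

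**4. Power against the 2-point limit, 4% in both groups.**

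- Non-inferiority, normal approximation: Φ(0.02/0.032 - 1.645) = 0.154 at one-sided 0.05; Φ(0.02/0.032 - 1.96) = 0.091 at one-sided 0.025.
- Non-inferiority, exact binomial enumeration at one-sided 0.05: 8% with Newcombe limits, 24% with Wald limits. With about two Fortiva events the method matters, but no version comes near 80%.
- Equivalence, if ±2 points is assumed: 0 (Newcombe) or 0.2% (Wald) by enumeration of 90% limits.
- Smallest limit with 80% non-inferiority power at one-sided 0.05: (1.645 + 0.842) × 0.032 = 8.0 points.

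**5. What the planned test would do.** Probability that chi-square gives p ≥ 0.05, by exact enumeration, Strattice at 4%:

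| True Fortiva rate | Uncorrected | Continuity-corrected |
|---|---|---|
| 6% | 89% | 94% |
| 8% | 76% | 85% |
| 10% | 61% | 73% |

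Example: 5/50 versus 6/150 (10% versus 4%) gives an uncorrected p = 0.107, with a 95% Newcombe interval of -1.2 to +17.6 points.

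**6. Complications.** The plan gives no rate or limit. At an assumed 10%, the 95% half-width is 1.96 × √[0.09 × (1/50 + 1/150)] = 9.6 points; at an assumed 30%, it is 1.96 × √[0.21 × (1/50 + 1/150)] = 14.7 points.

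**The case against.** The best defence is disclosure. The Sample Size text calls the study a pilot, gives 1188 per group as the confirmatory size and says that 200 is what is feasible. The goal and hypotheses can then be read as a long-term aim and an expectation, not a decision rule. No sentence says that a non-significant chi-square will be read as equivalence, and the open clause on other inference does not exclude an interval. Fortiva is already 510(k)-cleared, and surgeons may use it in patients who decline the study, so the result does not gate access. The plan sets no ±2-point equivalence limit, and the calculations ignore the matching.

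Much of this stands. The small sample is not itself a fault. The misreading is a risk, not a stated intention. The equivalence sample sizes and powers rest on an assumed two-sided limit. Within-set correlation would change the standard error somewhat.

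It does not remove the inconsistency. The Design sentence says what this study's comparison is for, and nothing in Sample Size withdraws it. A clause allowing further analysis as appropriate commits to no interval and no margin. The Goal section itself links the result to justifying use. Treating the groups as independent follows the plan's own unmatched chi-square, and the 90% half-width of 5.3 points is more than twice the 2-point limit.

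**Conclusion.** The point holds: the plan is wrong as written. It promises an equivalence conclusion that its named between-group test cannot support, and the sample is far below what its own benchmark requires for the weaker claim of non-inferiority. At 4% in both groups, power for the 2-point non-inferiority limit is roughly 8% to 24% depending on method (one-sided 0.05). If Fortiva's recurrence were double Strattice's, the planned test would still be non-significant about three times in four. These figures assume independent groups and full follow-up; losses would widen the intervals. The pilot is best described as not powered for non-inferiority or equivalence, since a favourable interval is improbable but not impossible.

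The beta label is a plain error with no effect on the sample size. The main point should be corrected before results are known, because rewording the goal afterwards would look driven by the data.

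**What to change.** Amend the wording in five places:

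- **Goal and Objectives:** replace the aim of showing equivalence, and both equivalence hypotheses, with: *to estimate the differences in recurrence and mesh-related complication rates with 95% confidence intervals; no equivalence conclusion will be drawn from this pilot.* Equivalence may remain as the aim of a later, adequately sized study if labelled as such.
- **Design:** state that the rates will be compared by estimating the difference with a 95% confidence interval.
- **Sample Size:** *With one-sided alpha 0.05, power 0.80 (beta 0.20), 1:1 groups, 4% recurrence in both and a 2-point non-inferiority limit, 1188 per group would be needed. This is a benchmark only. With 50 versus 150 and 4% in both groups, the expected 95% interval for the difference is about -5 to +10 points (Newcombe), so this pilot is not powered to establish non-inferiority or equivalence.*
- **Analytical Plan:** report both outcomes as risk differences with 95% intervals suited to sparse events (Newcombe is one example), say how the interval treats the matching, and state that a non-significant chi-square will not be interpreted as evidence of equivalence.

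The cost is a text amendment and one interval per outcome from data already being collected, with no added patients, visits or data items. The downside is a more modest stated goal: the pilot could no longer be presented as showing equivalence.

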### **Interventions and Interactions**

This study will involve surgical ventral hernia repair utilizing a biologic hernia mesh (Fortiva). Fortiva mesh may be used by a CLASP surgeon in ventral hernia repair in patients even if they choose not to participate in the research study.

- This study will involve the implantation of RTI Surgical Fortiva biologic mesh in the reconstruction of the abdominal wall. Mesh size, position, location and procedure will be determined and performed by an attending surgeon from Carolinas Laparoscopic & Advanced Surgery Program (CLASP).
- Study participants will be asked to follow up for at least 36 months.
  - Follow up will include participants being seen back in clinic as part of our standard of care after a ventral hernia repair or contacted via telephone at 2-weeks, 6-months, 1-year, 2-year, 3-year to evaluate the participants progress and recovery using the Fortiva mesh

Data elements to be collected are listed below:

Protocol version: 5

- Age
- Sex
- Race
- Body mass index (BMI)
- Comorbidities
  - Asthma
  - Cirrhosis
  - Congestive heart failure (CHF)
  - COPD
  - Coronary Artery Disease
  - Current Steroid Use
  - Current Anticoagulant Use
  - Diabetes history
  - Hemoglobin A1c
  - End Stage renal Disease
  - History of Cancer
  - Hypertension
  - Obstructive Sleep Apnea
  - Peripheral Vascular Disease
  - Smoking history
  - Current smoking status
  - Stroke History
  - Transplant patient
- Hernia defect size
- At the time of Surgery
  - Fistula present(y/n)
  - Mesh infection(y/n)
- Mesh size
- Mesh type
- Mesh location (preperitoneal, intraperitoneal, inlay/bridging, retrorectus, onlay)
- Number of hernia failures
- Number of hernia procedures
- Type of hernia procedures (emergent vs elective)
- Dates of Surgery
- Use of botox (y/n)
- American Society of Anesthesiologist (ASA) Classification
- Operative findings
  - Complete Fascial closure(y/n)
  - Enterotomy
- Use of component separation techniques (external oblique release or transversus abdominus release) to enable closure
- Length of Operation
- Recurrence(y/n)
- TAPP block
- Mesh resection
- Concomitant procedures
- Concurrent panniculectomy
- Mesh fixation (sutures/glue/none)
- Delayed primary skin closure(y/n)

- Wound complications(y/n)
  - Wound cellulitis
  - Wound infection
  - Surgical site infection (SSI)
  - Superficial wound breakdown
  - Intra-abdominal abscess
  - Seroma requiring intervention
  - Mesh infection
- Length of Stay
- Mortality
- 30-day readmission
- Pulmonary failure (y/n)
- Post-operative follow-up time

### **Outcome Measure(s)**

This study will measure the rate of hernia recurrence and mesh related complications for patients undergoing VHR with RTI Surgical Fortiva biologic mesh compared with patients who underwent VHR with Strattec mesh.

### **Analytical Plan**

Results will be analyzed initially using descriptive statistics. Comparison between groups will be done using chi square tests for proportions, and t-tests or ANOVA procedures for continuous variables. Regression analysis will be performed to identify independent outcome predictors. Other inferential statistical analysis will be conducted as appropriate.

### **Human Subjects Protection**

#### **Subject Recruitment Methods**

Subjects will be recruited in the attending physician's clinic. The attending physician will present the study initially and if the patient is interested a member of the study team (attending physician, fellow, resident, research manager or research associate) will fully introduce the study via protocol and ICF. Subjects may also be recruited via telephone if they have already been seen in clinic and will not be seen again prior to surgery but may otherwise be a candidate for the study. Telephone calls will be made prior to the day of surgery. Patients contacted via telephone will be introduced to the study and, if interested, will be noted as such and asked to sign the ICF on the day of surgery.

No preference will be given to any sex, race, or ethnicity. Patients who meet the inclusion/exclusion criteria will be recruited with the same interest level. PHI will be kept confidential in the clinic as well as before and after telephone calls to gauge recruitment interest.

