#### **Informed Consent**

Signed informed consent will be obtained from each subject in the prospective group. Informed consent will be obtained by a member of the research team (PI, Co-I, fellow, resident, research manager, or research associate) in the clinic prior to the date of surgery. Informed consent may be obtained on the day of surgery, if the patient has been contacted previously prior to the day of surgery, via telephone, and has stated an interest in participating in the research study.

A full waiver of consent/assent and a waiver HIPAA authorization will be requested for patients in the retrospective group as their procedures and outcomes have already happened and reporting on the procedures and outcomes will not adversely affect the patient's care. Access to age in years and

office/clinic notes will be requested. Access to patient name, phone number and MRN will be the only identifying information requested. The study material is identifiable; however, study data will be linked by an identifier assigned to each participant and the identifier will be the only information maintained in the study data. The standard operating procedure for our group is to keep all study data in a locked suite, locked file cabinet, or electronically via password protection on a secure computer, on a secure network. Identifiers will be kept as part of the participants' medical record indefinitely. Access to this information is requested to identify patients who have already undergone VHR with Strattec mesh and would be of the retrospective cohort.

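### Emergency repairs reach the two arms by different routes, and urgency is neither matched on nor committed to for adjustment, so confounding of unknown direction is possible

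*Combined protocol and SAP*

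**What the plan says.** **Eligibility.** The inclusion criterion is "Ventral Hernia requiring surgical repair" in an adult. No urgency criterion applies to either arm.

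**Preoperative entry to the Fortiva arm.** Under Subject Recruitment Methods, "Subjects will be recruited in the attending physician's clinic". The alternative is a call: "Subjects may also be recruited via telephone if they have already been seen in clinic and will not be seen again prior to surgery". The timing is fixed: "Telephone calls will be made prior to the day of surgery". The Informed Consent section allows signature on the day itself only "if the patient has been contacted previously prior to the day of surgery".

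**Postoperative entry to the Fortiva arm.** The Design section allows a later approach to patients who received Fortiva "when it was not otherwise planned (i.e. the surgeon changed the plan intraoperatively". A full waiver is to be requested for those who cannot be reached, with the stated aim of capturing everyone and avoiding skew.

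**Strattice arm.** It is retrospective, and Informed Consent requests a full waiver for it.

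**Retrospective Fortiva patients.** The Sample Size paragraph describes the 50 Fortiva patients, in a parenthesis, as partly retrospective. Design describes Fortiva patients as enrolled prospectively, and Informed Consent ties the retrospective cohort to Strattice.

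**Use of urgency.** The data list includes "Type of hernia procedures (emergent vs elective". The 1:3 propensity match uses age, sex and defect size. The Analytical Plan gives chi-square and t-tests or ANOVA, and a regression to find outcome predictors with no covariates named.

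**The concern.** The preoperative routes all presuppose contact before the day of operation. They suit scheduled surgery and not a patient who arrives acutely. The postoperative route could have closed that gap, but its wording ties it to a change of plan in theatre. The Strattice arm passes through no such filter.

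The protocol itself treats urgency as relevant. Its Background section separates elective repair, where mesh is strongly recommended under stated conditions, from emergent repair, where there is no conclusive recommendation. If urgency affects recurrence or wound and mesh complications, a different urgency mix could create or hide a difference between meshes. The study's stated goal is to show equivalent outcomes so as to justify using Fortiva, so either error matters. Such a bias does not shrink with more patients and would carry into a larger study modelled on this pilot.

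**Working it through.** **1. Entry routes side by side**

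| Patient | Clinic or call before surgery | After surgery, with waiver | From records |
|---|---|---|---|
| Fortiva, seen in clinic beforehand | Yes | Not needed | - |
| Fortiva, chosen in theatre, elective or emergency | Not relied on | Yes | - |
| Fortiva, first presents as an emergency, mesh planned beforehand | No | No | Only if the Sample Size parenthesis is meant to operate |
| Strattice, elective or emergency | - | - | Yes |

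The third row is the gap. It is narrow, but Strattice has no counterpart to it.

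**2. The plan's own figure.** Inputs from Sample Size: recurrence 4%, limit 2 points, alpha 0.05, and 0.80 (written as beta, read here as power). With alpha one-sided and 4% in both arms:

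n = 2p(1 − p)(z₀.₉₅ + z₀.₈₀)² / δ² = 2 × 0.04 × 0.96 × (1.6449 + 0.8416)² / 0.02² = 192 × 6.1826 = 1187.05, rounded up to 1188 per group.

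This matches the stated 1188, so 4% and 2 points are sound reference values.

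**3. Illustrative shift in recurrence.** The documents give no emergency share for either arm and no recurrence by urgency, so the following are assumptions. Let eS and eF be the emergency shares in the Strattice and Fortiva arms, RR the emergency-to-elective risk ratio, and the meshes identical. Holding overall Strattice recurrence at 4%, the elective risk is r = 0.04 / (1 + eS(RR − 1)), and

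shift = (eS − eF) × r × (RR − 1).

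- eS = 10%, RR = 2, eF = 0: r = 0.04/1.1 = 3.64%; shift = 0.10 × 3.64 = 0.36 points.
- eS = 20%, RR = 2, eF = 0: r = 0.04/1.2 = 3.33%; shift = 0.20 × 3.33 = 0.67 points.

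The table gives the shift in points; positive values favour Fortiva.

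| eS | RR | eF = 0 | eF = eS/2 | eF = eS | eF = 1.5 eS |
|---|---|---|---|---|---|
| 5% | 1.5 | 0.10 | 0.05 | 0 | −0.05 |
| 10% | 2 | 0.36 | 0.18 | 0 | −0.18 |
| 20% | 2 | 0.67 | 0.33 | 0 | −0.33 |
| 30% | 3 | 1.50 | 0.75 | 0 | −0.75 |

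With RR = 1 the shift is zero throughout. No comparable calculation is offered for complications, because the documents state no complication rate.

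**4. Scale.** At 50 versus 150 and 4% in both arms, the standard error of the difference is √(0.04 × 0.96 × (1/50 + 1/150)) = 0.032, or 3.2 points. Power for the 2-point limit is Φ(0.02/0.032 − 1.645) = Φ(−1.02), about 15%.

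**The case against.** A reader might infer that the arms will differ in urgency and that the comparison will favour Fortiva. The documents do not support that, for four reasons.

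- **The gap is narrow.** Design says biologic mesh is used in contaminated or dirty cases, and that this sometimes becomes clear only in theatre. Emergencies in which Fortiva is chosen there can enter afterwards, so a Fortiva emergency share of zero is an extreme case.
- **The direction could reverse.** The postoperative route could enrich the Fortiva arm for urgent or contaminated cases, which would count against Fortiva.
- **There may be another door.** The retrospective Fortiva wording in Sample Size could admit the missed cases from records. It appears once and conflicts with how Design and Informed Consent describe the arms, so it cannot be relied on until they are reconciled.
- **Urgency is recorded.** Imbalance can therefore be seen and adjusted for. The plan does not commit to doing so.

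It would also be tempting to treat 4% as the elective rate and obtain a shift of 0.4-0.8 points. The protocol gives 4% for Strattice without any split by urgency, so the calculation here holds it as the overall rate.

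Finally, any plausible shift is small beside a standard error of 3.2 points. That is fair for this pilot's precision, but it does not remove the bias. What stands is the missing route and the absence of any committed control for urgency. A claim about direction does not stand.

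**Conclusion.** The concern holds as a difference in entry routes combined with an uncontrolled covariate. Emergency patients with Fortiva planned beforehand have no stated prospective route, emergency Strattice patients can enter from records, and neither the match nor the planned analysis commits to handling urgency. Confounding is possible; its sign and size are unknown.

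The figure of 0.36-0.67 points, or 18-33% of the 2-point limit, is an illustration only. It rests on no Fortiva emergencies, 10-20% Strattice emergencies, doubled risk and 4% overall Strattice recurrence. Over the wider assumed range (5-30% Strattice emergencies, risk ratio 1 to 3, no Fortiva emergencies) it runs from 0 to 1.5 points. With a Fortiva share 1.5 times the Strattice share it runs from 0 to 0.75 points against Fortiva. The case for change is that the correction is cheap and works in either direction.

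**What to change.** 1. In Design, extend the postoperative consent and waiver route to every Fortiva repair that could not be approached before surgery, whether or not the mesh was planned. Align Subject Recruitment Methods and Informed Consent with it.
2. Add emergent versus elective to the matching, exactly or within the propensity model, using the field already collected.
3. In the Analytical Plan, name a regression that compares the meshes and includes urgency. At 4%, about 8 recurrences are expected in 200 patients (0.04 × 200), so the covariate list must be short and matching should do most of the work.
4. Report emergent and elective counts by arm, before and after matching.
5. Reconcile Sample Size with Design and Informed Consent on whether retrospective Fortiva patients exist and how they enter.

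The cost is a minor change to the consent and waiver request and a somewhat smaller pool of eligible Strattice matches. With exact matching, each Fortiva emergency needs three Strattice emergencies. Restricting both arms to elective repair would also equalise urgency, but it would change the study population and discard emergencies that the postoperative route can capture, so it is not needed to resolve this point.
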